### **5.1. SUBJECT DISPOSITION, DEMOGRAPHIC AND BASELINE CHARACTERISTICS**

Subject disposition will be presented for all patients in the FAS. The number of patients who completed the study or discontinued the study early will be provided. The reasons for early discontinuation from the study will be presented by treatment group. Similarly, descriptive statistics for end of treatment status (completed or discontinued) and the reasons for early discontinuation of study treatment will be presented.

Demographic and baseline characteristics will be summarized using the FAS population.

Demographic data reported by treatment group will include age, sex (at birth), race, ethnicity, and baseline body mass index (BMI) ( $\text{kg}/\text{m}^2$ ). This information will be reviewed for baseline differences, but no statistical testing will be performed.

To allow evaluation of baseline HS disease characteristics, descriptive statistics for the duration of HS disease (years) and the following continuous measures of baseline abscesses and inflammatory nodule count, baseline HS-PGA, and baseline PGA-SP rating will be summarized by treatment group. Additionally, the number and percentage of patients in each of the Hurley stages will be provided with patients categorized based on the worst grade from all anatomical locations.

Medical history conditions/events will be summarized using the system organ class and preferred terms coded with MedDRA version 24.0.

Findings from the screening physical examination (PE) will be summarized using the pre-specified body system categories and include reporting of abnormal not clinically significant and abnormal clinically significant.

The results of special labs collected at screening only (TB, Anti-CCP antibody, hepatitis B core antibody, hepatitis C antibody, HIV-12 AB, and SARS-CoV-2 virus) will be presented in listings.

### **5.2. PRIOR AND CONCOMITANT MEDICATIONS**

All medication (including vaccines, over-the-counter or prescription medicines, vitamins, and/or herbal supplements) taken from 14 days before start of screening until the end of the follow-up period will be recorded in the appropriate section of the eCRF.

Prior and concomitant medications will be coded using the WHO Drug Dictionary (version WHODrug - B3 Global March 2021) for the entire period of the study.

A summary by treatment for prior medications and a summary by treatment of concomitant medication will be provided for the FAS population. Each summary table will report the number (%) of patients by ATC classification using ATC level 2 and medication preferred term. Patients will be counted only once within each ATC and preferred term.

All prior and concomitant medications will be included in a subject data listing. Listings will distinguish medications as prior and/or concomitant.

### **5.3. STUDY DRUG EXPOSURE**

Study drug exposure and compliance will be summarized by treatment for the Safety population. The study drug treatment duration along with summaries of dose interruptions and treatment compliance will be reported.

The study drug dosing data collected in the subject diary will be provided in a data listing. Likewise, full accounting of the study drug dispensing, collection, and tablet counts will be provided in a data listing.

### **5.4. EFFICACY ANALYSIS**

All efficacy summaries will be conducted per SAP on both the FAS and PP Populations; analyses per the PP Population will be considered supportive.

All efficacy data will be presented in data listings.

#### **5.4.1. Primary Efficacy Endpoint**

The primary efficacy variable will be the change from baseline in abscess and inflammatory nodule (AN) count at Week 12 in the FAS population.

##### **5.4.1.1. Statement of Estimand**

The primary objective of this study is to assess the efficacy of ATI-450 50mg BID versus placebo in patients with moderate to severe HS. This efficacy assessment is intended to test the hypothesis that the ATI-450 treatment group is superior to placebo for the treatment of HS based upon the 12-week change from Baseline in inflammatory nodules and abscesses versus the null hypothesis of no difference. The following estimands (International Council for Harmonization [ICH] E9- R1) are defined to adequately achieve the intended primary objective for this study.

##### **5.4.1.2. Treatment**

The treatment condition of interest for this study is the fixed 12-week BID dosing of 50 mg of ATI-450 versus placebo. The administration of Protocol Excluded Medications/Treatments listed in the Protocol Appendix 5 for the purpose of rescue or as standard care following the discontinuation of study medication is strictly outside the treatment condition of interest for this study since they could confound or prohibit the determination of an optimal dose for ATI-450. Treatment durations less than 12-weeks based on the analysis visit windows, while providing supportive information, are, for the purpose of the primary estimand, outside the treatment condition of interest.

##### **5.4.1.3. Population**

The population of patients targeted by the clinical question of interest for this study includes patients with moderate to severe HS as defined by the inclusion and exclusion criteria who are randomized in the study and administered at least 1 dose of study drug.

##### **5.4.1.4. Variable**

The abscess and inflammatory nodule count at Week 12 was chosen as the variable (or endpoint) of our primary estimand because it is a well-established measure of the improvement in the signs and symptoms of HS. If the data to compute the primary endpoint is not collected, the endpoint will be imputed using the LOCF. Additionally, data collected after the occurrence of a confounding event (see Section 5.4.1.5) will not be used to calculate the primary endpoint. Instead, the endpoint will be imputed using the LOCF prior to the intercurrent event.

##### **5.4.1.5. Intercurrent Event Strategy**

Prior to week 12 lesion counts, the following are confounding intercurrent events that are likely to occur in some patients during conduct of the trial: 1) discontinuation of study treatment for any reason, 2) the administration of protocol prohibited medications listed in Appendix 5 of the

---

Protocol that could impact efficacy for any reason, and 3) surgical intervention. Determination of prohibited medications that could impact efficacy will be conducted in a blinded manner prior to database lock. Assessments that occur after a confounding event will be excluded from the analysis and imputed using the last observed assessment prior to the intercurrent event. The date/time of the confounding event and the start date/time of imputation will be determined based upon the last dose of study medication, the start date of any relevant prohibited medications, and the start date of any surgical procedures.

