7.2 Temporary Discontinuation

7.2.1 Unrelated Adverse Events or COVID-19 Diagnosis

If a drug is stopped temporarily due to a clearly unrelated adverse event, for example, treatment of a fracture caused by a motor vehicle accident or COVID-19 infection, dosing may be reinitiated, after discussion with the Medical Monitor, if the temporary discontinuation was shorter than a maximum of 14 days in the total 12-week treatment period. In exceptional circumstances, medical monitor may allow dosing to be resumed with a gap of up to 21 days. In all cases, if the dosing gap is in excess of 21 days, dosing should be discontinued permanently.

In case of a COVID-19 infection, consult study Medical Monitor to discuss risk/benefit considerations of patient continuing or discontinuing study medication treatment.

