#### **3.3.4. Missing Data and Outliers**

Analysis visit windows will be applied as indicated in [Section 3.3.7](#). If an efficacy assessment is not available in an analysis visit window, then last observation carried forward (LOCF) will be applied to obtain a value for that analysis visit window for analyses conducted on the full analysis set population. For categorical efficacy endpoints, an additional sensitivity analysis will be conducted using non-responder imputation for cases where an efficacy assessment is not available in an analysis visit window. Missing data will not be imputed for safety summaries or efficacy summaries on the per protocol population.

There are multiple reasons that an assessment may not be available within an analysis visit windows:

- Clinic visits out of window or missed visits

- Data excluded from use in analysis due to confounding intercurrent event (see [Section 5.4.1.5](#))

For the latter reason, any assessments that occur after a confounding intercurrent event will be considered missing for purpose of analyses.

For analysis visit windows without an assessment, regardless of the reason, the last non-missing value prior to the start of the analysis visit window will replace the missing values. The baseline assessment can be carried forward.

If an AE has missing relationship to the study drug or severity, then that AE will be considered as ‘related’ to the study drug and the severity will be considered as ‘Severe’ in the table summaries, but the AE will be displayed as having a missing relationship or severity in the listings

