## 7. REVISION HISTORY

Date	Revision	Rationale
18OCT2022	Updated sample size Schedule of assessments updated for PGA-SP [REDACTED] [REDACTED] [REDACTED]	Changes in protocol amendment
	Added details for imputation of alphanumeric data [REDACTED] [REDACTED]	Clarification
	Specified how missing AE relationship and severity will be handled in the summary tables Added definition of treatment-emergent	

Date	Revision	Rationale
	
laboratory toxicity and specified that CK, absolute neutrophils, ALT, AST and Bilirubin will be summarized by maximum toxicity grade
 
Specified the criteria for AESI
 
Specified that coagulation will be included in hematology tables and listings
 
Specified that triplicate averages will be summarized and used to determine if patients meeting noteworthy QT/QTcF criteria
 
Separate out QT and QTcF noteworthy tables
 
Specified how to choose ECG interpretation results amongst the triplicate values
 
Specified that both investigator and central ECG interpretation will be summarized
	
	Added PK figures to list of proposed figures	Consistency with text
	Removed PD analyses and outputs	Data will be presented in a separate report
	Updated numbering for some tables, listings, and figures	Consistency with ICH guidelines
16FEB2023	
Limited the prohibited medications considered to cause an intercurrent event to those that would impact efficacy.
 
Specified that these medications would be determined prior to database lock in a blinded manner
	Imputation of data following prohibited medication administration that would not impact efficacy is not appropriate.
	Added a one-sided Mood's median test to assess the impact of outliers, non-normality, and skewness of the data on the primary analysis.	To provide a sensitivity analysis of the impact of outliers, non-normality, and skewness of the data on the primary analysis.

---

Date	Revision	Rationale
	[REDACTED]	[REDACTED]
	[REDACTED]	[REDACTED]
	[REDACTED]	[REDACTED]
	Updated HiSCR to HiSCR50	Distinguish between HiSCR50 and the added endpoints

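### SAP 5.4.1.5 limits the prohibited-medication event to drugs that could affect efficacy but sets no such limit on surgery, so an operation with no bearing on lesion counts would replace a patient's later on-treatment data

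*SAP*

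**What the plan says.** SAP 5.4.1.5 names three confounding intercurrent events before the Week 12 lesion counts. The first is stopping study treatment. The second is a prohibited medication from Protocol Appendix 5, and the third is surgery. The list ends: "Protocol that could impact efficacy for any reason, and 3) surgical intervention". The efficacy condition belongs to the second event, and the blinded pre-lock determination described next covers prohibited medications only. The sentence that dates the events keeps the distinction: after the last dose of study medication, it names "the start date of any relevant prohibited medications, and the start date of any surgical procedures".

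The consequence appears in three places:

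- SAP 5.4.1.5: assessments after the event "will be excluded from the analysis and imputed using the last observed assessment prior to the intercurrent event".
- SAP 5.4.1.4, for the primary variable: "the endpoint will be imputed using the LOCF prior to the intercurrent event".
- SAP 3.3.4, for efficacy data generally: "any assessments that occur after a confounding intercurrent event will be considered missing for purpose of analyses". The same section adds: "The baseline assessment can be carried forward".

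The revision history in SAP section 7 explains why the medication event was narrowed on 16FEB2023: "Imputation of data following prohibited medication administration that would not impact efficacy is not appropriate".

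**The concern.** The reason given for narrowing the medication event applies equally to surgery. If it is wrong to impute after a drug that cannot affect efficacy, it is wrong to impute after an operation that cannot. The revision changed one event and left the other open.

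Stopping study drug is a separate event, so the surgery event also reaches a patient who keeps dosing and attends every visit. SAP 5.4.1.2 places two things outside the treatment condition of interest: excluded treatments from Appendix 5, given as rescue or as standard care after discontinuation, and treatment shorter than 12 weeks. On the visible text, a patient who completes 12 weeks of dosing and has an unrelated operation is in neither group. The estimand should therefore use that patient's Week 12 count, but the rule replaces it.

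No planned FAS efficacy analysis restores the count. The primary MMRM (SAP 5.4.2) and Mood's median test (SAP 5.4.3) both use last observation carried forward. The non-responder analysis covers any visit window without an available assessment, and SAP 3.3.4 lists intercurrent-event exclusions among the reasons for that. A patient who meets HiSCR50 at Week 12 after such an operation would be scored a non-responder there.

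**Working it through.** **Inputs** (Protocol 9.2, 9.1 and 1.1; SAP 3.1): mean reduction 4.75 on ATI-450 and 2.5 on placebo, difference 2.25; SD 3.6; 45 patients per arm; one-sided alpha 0.05; stated power 90.3%. No rate of unrelated surgery is given, so the numbers affected below are assumptions.

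**Step 1: reproduce the plan's figure.** Standard error = 3.6 × √(2/45) = 0.759. Noncentrality = 2.25 / 0.759 = 2.96. The noncentral t with 88 degrees of freedom, one-sided 0.05, gives 90.27%, which matches 90.3%. The power calculation is not in dispute.

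**Step 2: effect of one affected patient.** If baseline is carried forward, the analysed change is 0. The expected shift in the arm mean is:

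- ATI-450: 4.75 / 45 = 0.106 lesions
- Placebo: 2.5 / 45 = 0.056 lesions

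**Step 3: effect on the difference and on power.** Let q be the share of an arm affected, f the fraction of the Week 12 change already present in the carried count, and μ the arm's assumed mean reduction.

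- Arm mean: m = μ(1 − q + qf).
- Arm variance: (1 − q)(3.6² + μ²) + q(v + (fμ)²) − m², with v = 0 when baseline is carried and v = 3.6² when f = 0.5.

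Example, one patient per arm (q = 1/45) with baseline carried:

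- Means: 4.75 × 44/45 = 4.644 and 2.5 × 44/45 = 2.444, difference 2.20.
- Variances: 13.16 and 12.81.
- Standard error: √((13.16 + 12.81)/45) = 0.760.
- Noncentrality: 2.20 / 0.760 = 2.90, power 89.0%.

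The same calculation for other assumed cases gives:

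| Affected patients (assumed) | Baseline carried: difference, power | Half the change already present: difference, power |
|---|---|---|
| None | 2.25, 90.3% | 2.25, 90.3% |
| 1 per arm | 2.20, 89.0% | 2.225, 89.5% |
| 2 per arm | 2.15, 87.7% | 2.20, 88.8% |
| 10% of each arm | 2.025, 84.2% | 2.14, 86.8% |
| 2 on ATI-450 only | 2.04, 84.2% | 2.14, 87.4% |
| 2 on placebo only | 2.36, 92.8% | 2.31, 91.4% |

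Equal numbers per arm shrink the difference slightly. Unequal numbers can move it in either direction.

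**The case against.** The strongest defence is that the SAP means surgery for hidradenitis. It calls the events confounding, and the phrase about any surgical procedures stands in a sentence that only dates events, so it could refer to operations already classed as confounding. SAP 5.4.1.2 also speaks of rescue and standard care, which suggests disease-directed treatment. This is a possible reading of intent. But surgery is not defined in the text I could read, and the dating sentence qualifies medications as relevant while writing any for surgery. A programmer following the text would include every operation, and settling the meaning after unblinding would be a post hoc choice.

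A definition in text I could not read cannot be ruled out: Appendix 5 was not available, and parts of Protocol 6.5, SAP 3.3.7 and SAP 6 are redacted. However, the SAP cites Appendix 5 for the medication event and not for the surgery event.

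Three stronger readings are tempting, and the documents do not support them:

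- **That the plan expects unrelated operations.** Protocol 7.2.1 mentions "treatment of a fracture caused by a motor vehicle accident or COVID-19 infection, dosing may be reinitiated". It shows that dosing can resume after an unrelated event. It does not say that the treatment is surgical.
- **That the primary result is materially biased.** Assume three affected ATI-450 patients, none on placebo, the Day 15 count carried and improvement linear in time. Then 5/6 of the change is lost (14 of 84 days have elapsed), and the difference falls by 3 × 4.75 × (5/6) / 45 = 0.264, or 0.264 / 2.25 = 12%. That is one selected imbalance with no supporting rate. The balanced cases are much milder, and a placebo-only imbalance goes the other way.
- **That data are lost.** SAP 5.4 puts all efficacy data in the listings. The counts leave the analyses but can still be examined.

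**Conclusion.** The point holds as a defect in a stated rule. SAP 5.4.1.5 applies an efficacy test to medications and none to surgery. Followed literally, it imputes over valid on-treatment assessments in a situation that the SAP's own revision rationale calls inappropriate. Neither the confounding label nor the reference to Appendix 5 supplies the missing limit.

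The size is probably small, on the assumption that few of about 90 patients have an unrelated operation within 12 weeks. With one or two per arm and baseline carried, the least favourable carry-forward considered here, power falls by about 1 to 3 points, from 90.3% to 89.0% or 87.7%. If half of the Week 12 change is already in the carried count, power is 89.5% or 88.8%. These figures use the plan's own means and SD and the two-sample comparison that reproduces its power, not the MMRM itself. They show scale and do not forecast an effect on the result.

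**What to change.** Make three changes in SAP 5.4.1.5, before unblinding:

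1. Reword event 3 as *surgical intervention that could impact efficacy (lesion counts)*.
2. In the dating sentence, write *any relevant surgical procedures*.
3. Include surgical procedures in the blinded pre-lock review already planned for prohibited medications.

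The test should be whether the procedure could affect lesion counts, as it is for medications. Limiting the event to operations on hidradenitis lesions or affected areas would be too narrow, because a procedure elsewhere that could still affect the counts would then escape the rule.

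The cost is two phrases, a short extension of an existing review, and one blinded judgement per procedure. Sample size and data collection do not change.

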#### **5.4.1.6. Population-Level Summary**

The population-level summary for this study will be the model-based treatment difference and corresponding p-value for the change from baseline in inflammatory abscesses and nodules. The statistical model will be a mixed effect for repeated measures (MMRM) model that includes fixed factors for treatment group, visit, treatment by visit interaction, and baseline abscess and inflammatory nodule count. Patient identifier will be included in the model in a manner that allows observations within a given patient over time to be treated as repeated measures. The ATI-450 treatment group will be compared with placebo; the model-based estimate for the difference in least squares mean (LS Means), 90% confidence intervals (CIs), and one-sided p-value will be calculated.

#### **5.4.2. Primary Efficacy Analysis**

Descriptive statistics for the count and change from baseline in the inflammatory abscesses and nodules will be presented for each scheduled analysis visit. This primary analysis will utilize the count with imputation for LOCF and will be based on the FAS population. Change from baseline in count of inflammatory abscesses and nodules up to Week 12 will be analyzed using a MMRM model. The model will include fixed effect terms for treatment, study visit, treatment by visit interaction and baseline count of inflammatory abscesses and nodules. Patient identifier will be included in the model in a manner that allows observations within a given patient over time to be treated as repeated measures. Within-subject variability will be modeled using a compound symmetry covariance structure. The LS Mean change from baseline in the count at each visit, estimated from the MMRM model, with the estimated standard error and 90% CI, will be presented in tabular and graphic format. The difference in the adjusted means between treatment groups and the associated 90% CI of the difference will be provided.

The model results from Week 12 are the primary efficacy analysis.

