#### **5.4.3. Supportive Analysis of Primary Efficacy Endpoint**

The statistical methods with LOCF for the main analysis will be repeated using the PP population.

A one-sided Mood's median test will be used to compare the treatment groups for the primary endpoint of change from baseline in AN count with LOCF. This test will be conducted at each

analysis visit separately. Only the one-sided p-values and associated medians for each group will be presented for this non-parametric test (no confidence intervals).

For each of the subsets defined in [Section 3.3.2](#), the primary efficacy MMRM analysis will be performed. If there are not enough patients in a subset to perform the MMRM, then descriptive statistics only will be presented for that subset.

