#### **5.4.5. Secondary Efficacy Analysis**

##### MMRM Analyses

For continuous efficacy measures IHS-4, HS-PGA, and DLQI, the descriptive statistics for the calculated scores and the change from baseline in the scores will be reported for each analysis visit at which the assessment was planned for collection.

The change from baseline in the IHS-4, the change from baseline in DLQI, and change from baseline in HS-PGA will be analyzed for inferential results using the methods planned for the primary efficacy analysis with LOCF.

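### The primary MMRM fixes compound symmetry, so the Week 12 test uses a variance averaged over six visits: the 5% level is exceeded if Week 12 is more variable than average, and power is lost if it is less variable

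*SAP*

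**What the plan says.** SAP 5.4.2 fits an MMRM to the change from baseline in abscess and inflammatory nodule count. The fixed effects are treatment, visit, treatment by visit and baseline count. It then fixes the covariance: "Within-subject variability will be modeled using a compound symmetry covariance structure". It also says: "The model results from Week 12 are the primary efficacy analysis".

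The model has six post-baseline visits (Days 8, 15, 29, 43, 57 and 85). The primary analysis uses LOCF on the FAS, and under SAP 3.3.4 "The baseline assessment can be carried forward", so each patient has a value at all six.

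The protocol (9.4.1, Table 5) asks only that visits within a patient be treated as repeated measures. The choice of structure was made in the SAP.

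The same model is used elsewhere:
- PP population (5.4.3): "The statistical methods with LOCF for the main analysis will be repeated using the PP population".
- Subsets (5.4.3), with an escape clause: "If there are not enough patients in a subset to perform the MMRM, then descriptive statistics only will be presented for that subset".
- IHS-4, HS-PGA and DLQI (5.4.5), which "will be analyzed for inferential results using the methods planned for the primary efficacy analysis with LOCF".

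The one supportive analysis of another kind is a one-sided Mood's test (5.4.3): a "median test will be used to compare the treatment groups for the primary endpoint of change from baseline in AN count". The revision history gives its purpose: "To provide a sensitivity analysis of the impact of outliers, non-normality, and skewness of the data on the primary analysis".

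**The concern.** Compound symmetry assumes one variance and one correlation for every visit from Day 8 to Day 85. The primary question concerns Day 85 alone. Nothing in the documents supports equal variances: they give a single SD of 3.6 and none by visit.

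If the adjusted counts are more variable at Week 12 than on average, the model's standard error is too small and superiority is declared too easily. If they are less variable, the standard error is too large and power is lost. With balanced data the point estimate is essentially unaffected. The p-value and the interval are at stake.

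No visible text offers another structure, a robust standard error or a covariance sensitivity analysis.

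**Working it through.** **Inputs from the documents.** 45 patients per arm; mean reductions 2.5 and 4.75, so a difference of 2.25; SD 3.6; one-sided alpha 0.05; 90% CI (SAP 3.1, 5 and 5.4.2; protocol 9.1 and 9.2).

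**Stated power.** SE = 3.6 × sqrt(2/45) = 0.759, and 2.25/0.759 = 2.965. The normal approximation gives Phi(2.965 − 1.645) = 90.7%. The noncentral t with 88 df gives 90.27%, which matches the stated 90.3%. That figure is for a single-visit t test, not for the compound symmetry model.

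**Why the variance is averaged.** Let S be the true 6 × 6 residual covariance matrix and n = 45. With every visit filled, the compound symmetry fit uses two mean squares:
- MSb, the variance of patient means, with expectation (sum of all elements of S)/36;
- MSw, the within-patient variance, with expectation [trace(S) − (sum of all elements)/6]/5.

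The model's squared standard error at Week 12 is about (2/n) × [MSb + (5/6) × MSw]. The sums of all elements cancel, leaving (2/n) × trace(S)/6, the average of the six variances. The true squared standard error is (2/n) × the Week 12 variance.

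**Consequence.** With V = Week 12 variance / six-visit average:
- one-sided level = 1 − Phi(1.645/sqrt(V));
- 90% CI coverage = 2 × Phi(1.645/sqrt(V)) − 1;
- power = Phi(2.965 − 1.645/sqrt(V)), taking 3.6 as the adjusted Week 12 SD.

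| V | Level | Coverage | Power |
|---|---|---|---|
| 0.7 | 2.5% | 95.1% | 84.1% |
| 0.8 | 3.3% | 93.4% | 87.0% |
| 1.0 | 5.0% | 90.0% | 90.7% |
| 1.2 | 6.7% | 86.7% | 92.8% |
| 1.5 | 9.0% | 82.1% | 94.8% |

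The extra power above V = 1 comes from the inflated level.

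**What V might be (assumptions).** The correlation between counts t weeks apart was set to c × exp(−lambda × t). Here c is the correlation of two counts taken very close together (0.9, 0.8 or 0.7), and lambda makes the baseline/Week 12 correlation 0.3, 0.5 or 0.7. The count SD was constant or fell linearly by 15, 25 or 35% by Week 12. One baseline slope was used for all visits, as in the SAP model.

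| Fall in count SD | Level over the 9 patterns |
|---|---|
| none | 5.0–9.3% |
| 15% | 3.6–7.9% |
| 25% | 2.7–6.9% |
| 35% | 1.9–5.8% |

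V runs from 0.63 to 1.54. Of the 36 patterns, 14 have a level between 4% and 6%, 16 are above 6% and 6 are below 4%. These counts are not probabilities, and the grid is not a bound. With constant SD and c = 1, the simulated level was 9.6–12.1%.

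**Simulation.** REML compound symmetry with Satterthwaite df was compared with an unstructured covariance, 16,000 trials per pattern. The unstructured fit used 88 df as an approximation to Kenward-Roger.

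| V | Level, compound symmetry | Level, unstructured | Power, compound symmetry | Power, unstructured |
|---|---|---|---|---|
| 1.54 | 9.5% | 5.1% | – | – |
| 0.78 | 3.1% | 5.0% | 85.8% | 91.0% |
| 0.63 | 1.8% | 4.9% | 81.4% | 91.8% |

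Over all 18 patterns simulated, the unstructured level was 4.8–5.4% and its power 88.0–91.9%.

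**Robustness of the rule.** With skewed counts (negative binomial margins, baseline at least 5), simulated compound symmetry levels were within 0.4 points of the rule. With 20% dropout and LOCF, they ranged from 2.3% to 9.2% over eight patterns, within 0.5 points of the rule's values for the same patterns without dropout.

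**The case against.** The strongest reply is that no error is shown for this trial. V is unknown, V = 1 means no fault, and 14 of the 36 assumed patterns stay within a point of 5%. Compound symmetry was pre-specified, and this is a Phase 2a study at one-sided 0.05 without multiplicity adjustment. All of that is true and limits the weight of the point. It does not justify fixing an equal-variance assumption that the documents do not support when a standard choice avoids it.

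Two partial safeguards exist:
- The SAP reports descriptive statistics, including the SD, at each visit. Unequal variances would be visible, but only afterwards and without baseline adjustment, and the primary p-value would stand.
- Mood's test is applied to change from baseline at each visit and does not use the pooled variance. It has no baseline covariate, compares medians, gives no interval and is supportive only.

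Other limits also stand:
- SAP Section 6 and parts of the revision history are redacted, so the absence of an alternative can be asserted only for the visible text. Sections 5.4.2 and 5.4.3 show no redaction.
- An unstructured matrix can fail in very small subsets; at about 4 patients per arm it was singular in some simulated trials.
- DLQI has three post-baseline visits, so the six-visit average does not describe it.

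**Conclusion.** The concern holds and should be fixed, at no higher grade than that for a Phase 2a study. In the FAS, the Week 12 standard error, p-value and 90% CI depend on a six-visit average variance and are wrong whenever V differs from 1. The mechanism is certain; the size and direction for this trial are not. Under the 36 assumed patterns the one-sided level runs from 1.9% to 9.3%, and it goes higher if two counts taken close together are almost perfectly correlated. The power figures assume an adjusted Week 12 SD of 3.6.

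The rule is claimed for the FAS only, because SAP 3.3.4 rules out imputation in the PP population while 5.4.3 repeats the LOCF method there. The effect on the PP, subset, IHS-4, HS-PGA and DLQI models was not quantified.

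**What to change.** In SAP 5.4.2, replace compound symmetry with an unstructured covariance and Kenward-Roger degrees of freedom. Pre-specify the order if it does not converge: heterogeneous Toeplitz, then heterogeneous compound symmetry. Both keep a separate variance for each visit. Apply the same wording to the PP and subset models in 5.4.3 and to IHS-4, HS-PGA and DLQI in 5.4.5. If no listed structure converges in a subset, the existing descriptive-only rule applies. For the other models the SAP should name a last step; a Week 12 ANCOVA on baseline would also remove the dependence on V. Compound symmetry may be kept as a sensitivity analysis.

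The cost is SAP wording only. The model estimates 6 × 7/2 = 21 covariance parameters instead of 2 (3 × 4/2 = 6 for DLQI), which is feasible with about 90 patients and LOCF-completed visits. In a check with 20% dropout and LOCF at 45 per arm, the unstructured level was 4.7% and 5.4%. Small subsets may need the fallback, and the interval will be wider if V is above 1.
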